The initial cocaine-vs-placebo session will be conducted to demonstrate that this dose of cocaine functions as a reinforcer in each subject and will also serve as a medical safety session. Subjects exhibiting cardiovascular hypersensitivity will be excluded from further participation. Cardiovascular hypersensitivity is defined as heart rate $>$ (220-subject age) \times 0.85, systolic pressure $>$ 180 mm Hg or diastolic pressure $>$ 120 mm Hg, or ECG abnormalities, sustained for greater than 5 min. If vital signs are elevated above these criteria, the nurse or physician will re-assess using the automated machine at minute intervals for 5 total readings. If vital signs remain above these criteria for all 5 readings, a manual reading will be taken. If vital signs are still elevated, a subject will not receive further doses, will be followed until symptom resolution, and will be excluded from further research participation. Cardiovascular hypersensitivity also includes prolonged abnormal heart rhythmicity assessed via 3-lead telemetry. Abnormal heart rhythmicity during experimental sessions is defined as ventricular arrhythmias that occur at a frequency greater than 5 per minute, are multifocal, or occur as couplets (2 consecutive beats) or salvos (3 or more consecutive beats), and persist for greater than 5 min. A cardiovascular emergency will be managed using UK medical center procedures (i.e., response from a code blue team).

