Heart rate will be measured continuously during experimental sessions and will be reviewed prior to each dose to ensure that the dosing criterion is met. Subjects must have a heart rate of $<$ 130 bpm to receive a dose, otherwise dosing will be paused. Due to the time required for the blood pressure reading to occur (i.e. cuff inflation and deflation) and the recommended 1-min interval between assessments, measuring BP before each infusion is incompatible with the infusion delivery schedule. Because of these limits on measuring BP in relation to dosing, BP will be assessed at 2-min intervals. If, following any BP assessment, systolic blood pressure \geq 165 mm Hg or diastolic blood pressure \geq 100 mm Hg, dosing will be paused. Subjects will also be connected to 3-lead telemetry so that ECG can be assessed at the beginning and end of the experimental sessions. Subjects must exhibit normal heart rhythmicity for intravenous dosing to be initiated (pre-session ECG assessment) and to participate in further sessions (post-session ECG assessment). If cocaine dosing stopping criteria are met, the task will be paused, and vital signs will be monitored by ACLS-certified nursing staff every minute until dosing criteria are met. If dosing criteria are not met within 10 minutes, a physician and the study PI will be contacted for further instructions. If a subject exhibits cardiovascular sensitivity to cocaine, the procedures described above will be followed, and continuous ECG monitoring will be initiated for a minimum of 5 minutes to determine if abnormal heart rhythmicity is accompanying the elevated HR/BP. If dosing criteria are not met by the scheduled end of the session, but cardiovascular sensitivity criteria are also not met, a study physician will be consulted about possible discontinuation of the subject from the protocol.

Volunteers will be free to engage in recreational activities (e.g., watch television, read, listen to music, arts and crafts, play video or board games) during non-session times. Research volunteers will be required to be in bed with the lights out by 2300 hours.

Study Outcomes (Inpatient Experimental Sessions)

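### Ventricular arrhythmia during a session is an exclusion criterion, but routine in-session rhythm review and a rhythm-based dose hold are not specified

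*Combined protocol and SAP*

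**What the plan says.** **The criterion.** RESEARCH PROCEDURES sets the consequence: "Subjects exhibiting cardiovascular hypersensitivity will be excluded from further participation". It then brings rhythm into that definition: "Cardiovascular hypersensitivity also includes prolonged abnormal heart rhythmicity assessed via 3-lead telemetry". The pattern is specific: "Abnormal heart rhythmicity during experimental sessions is defined as ventricular arrhythmias that occur at a frequency greater than 5 per minute", or that are multifocal or come as couplets or salvos, lasting more than 5 min. No HR or BP condition is attached.

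**The schedule.** HR is recorded continuously and "will be reviewed prior to each dose to ensure that the dosing criterion is met". For pressure, "BP will be assessed at 2-min intervals". For rhythm, subjects are "connected to 3-lead telemetry so that ECG can be assessed at the beginning and end of the experimental sessions". The Physiological measures paragraph gives the same timing: HR continuous, BP every 2 min, ECG before and after the session.

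**The actions.** Dosing pauses if HR is not below 130 bpm, systolic BP is 165 mm Hg or more, or diastolic BP is 100 mm Hg or more. Normal rhythm is needed to start dosing and again "to participate in further sessions (post-session ECG assessment"). If cardiovascular sensitivity appears, continuous ECG is started for at least 5 min "to determine if abnormal heart rhythmicity is accompanying the elevated HR/BP".

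**Other safeguards.** Physiological measures has telemetry-certified nurses interpret the recordings and call a physician about abnormalities. SAFETY PRECAUTIONS puts subjects under direct nurse supervision during dosing and under physician monitoring throughout participation. It also refers back to the earlier text for the criteria for holding and resuming doses.

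**The concern.** The exclusion concerns what happens during the session, whereas the scheduled ECG assessments fall at its two ends. An arrhythmia can begin after the first ECG, last more than 5 min and settle before the second. A subject who met the exclusion could then finish dosing, pass the post-session ECG and go on to another cocaine session. The event would also be missing from the count of cardiovascular discontinuations in stopping rule 3.

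The second part of the concern does not depend on anyone missing the rhythm. HR and BP have limits that stop dosing well before their exclusion thresholds. Rhythm has an exclusion threshold but no earlier hold, so nothing written tells staff to withhold cocaine while the 5 min are running. The protocol itself lists arrhythmias among the common side effects of cocaine (POTENTIAL RISKS), so this is a foreseeable event.

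**Working it through.** The plan states no figure to reproduce. The check sets the provisions side by side and then sizes the exposure.

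**Step 1. Provisions for each measure during dosing**

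| Measure | Can exclude a subject | Scheduled review during dosing | Limit that pauses dosing |
|---|---|---|---|
| HR | above 0.85 × (220 − age), sustained over 5 min | before each dose | not below 130 bpm |
| BP | systolic above 180 or diastolic above 120 mm Hg, sustained over 5 min | every 2 min | systolic ≥ 165 or diastolic ≥ 100 mm Hg |
| Rhythm | defined ventricular pattern, over 5 min | none between the pre- and post-session ECGs | none |

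**Step 2. Does the triggered ECG fill the gap?** Only in part. It is *initiated* after sensitivity appears, which implies that continuous ECG review is not already running. Its stated purpose is to see whether abnormal rhythm accompanies raised HR/BP. An arrhythmia with HR and BP within limits does not clearly set it off.

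**Step 3. Number of scheduled reviews in a drug-versus-money session.** Inputs from Probabilistic Reinforcement-Learning Choice Tasks: about 37 min and a maximum of about 39 infusions.

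- HR: one review before each dose, so up to about 39.
- BP: 37 / 2 = 18.5, so about 18 readings.
- Rhythm between the two ECGs: 0.

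These are scheduled entries. They do not count how often staff look at the monitor. The 37 min is task length, so if the ECGs are taken before and after the task, the interval between them is at least that long.

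**Step 4. Cocaine that could be given while the 5 min run**

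- Choice task: 39 / 37 = 1.054 infusions per min. Over 5 min, 1.054 × 5 = 5.27 infusions, and 5.27 × 3 mg/70 kg = 15.8 mg/70 kg.
- Safety session (Medical Safety Session: 1 min between trials): at most about 5 infusions in 5 min if cocaine is chosen every time, and 5 × 3 = 15 mg/70 kg. Choice and infusion time would lower this.

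Both are ceilings. They assume the maximum rate and no intervention for the full 5 min.

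**The case against.** The best counter-argument is that a rule about arrhythmias per minute, lasting more than 5 min during sessions, can only be applied by someone watching telemetry. On that reading the hypersensitivity paragraph is itself the monitoring provision, and the pre- and post-session ECGs are formal gates for starting dosing and for entering the next session. The hypersensitivity definition also lists ECG abnormalities alongside HR and BP, so the trigger for continuous ECG is not unmistakably limited to HR/BP. For harm to follow, an arrhythmia would have to last over 5 min, cross no HR or BP limit, go unnoticed by nurses supervising dosing directly, and clear before the post-session ECG.

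Much of this stands. A reader might infer that rhythm goes unmonitored during sessions. The documents do not support that: subjects are on telemetry, an in-session ECG review exists once sensitivity appears, and certified nurses interpret and escalate. A reader might also take about 5 infusions as the expected exposure. It is an upper limit in a probabilistic task with a money alternative, and a nurse who sees the rhythm is told to call a physician.

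Two things survive. The only stated timing for routine ECG assessment, given twice, is before and after the session, and no sentence asks for rhythm review during dosing. Even under the favourable reading, no rule holds doses while the criterion is being met.

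A further objection concerns the remedy. If a single couplet paused dosing and every such pause counted under stopping rule 2, the trial could be halted on little evidence: that rule can apply once 6 subjects have each had one dosing session, and 2 / 6 = 33.3%, which already exceeds 33%. That is a fair warning and the fix takes account of it.

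**Conclusion.** The point holds for *routine* in-session rhythm review and for a rhythm-based dose hold. Followed as written, the ECG schedule cannot reliably detect the protocol's own in-session exclusion, and dosing has no written hold while that exclusion is being established. The size is 0 scheduled rhythm reviews between the two ECGs and, at most, about 5 infusions (about 16 mg/70 kg) during the 5 min.

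This rests on reading the stated ECG timing as the complete routine schedule. Staff may well watch the monitor in practice, and the session forms are not available to check. How often such an arrhythmia would occur, or go unnoticed, cannot be derived from the documents, so no rate of harm is claimed.

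It is a safety-monitoring gap. A reader might infer that it undermines the results, but the Data Analysis Plan analyses the number of drug choices and nothing here shows an effect on that analysis. The text should be changed; confidence is medium because of the ambiguity described above.

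**What to change.** 1. In RESEARCH PROCEDURES and Physiological measures, state that the telemetry-certified nurses already assigned watch telemetry rhythm continuously throughout IV dosing. Keep the pre- and post-session ECGs as gates.
2. Add to the pause criteria in RESEARCH PROCEDURES that dosing is held while the defined ventricular pattern is ongoing and resumes once rhythm is normal. If the pattern lasts more than 5 min, the existing exclusion applies.
3. Have the study physician set the hold threshold, so that one isolated couplet need not trigger it.
4. State in Study Stopping Criteria whether rhythm holds count toward the 33% pause limit in rule 2, instead of adding them by default. Rule 3 already covers discontinuations for rhythm and needs no change.

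**Cost.** Mainly protocol wording, since telemetry is already connected and the nurses are already assigned. The downside is more nurse attention to the monitor and possibly some additional pauses that interrupt the choice task. The documents give no rate from which to estimate how many.

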participation. Subjects could be observed by a same-sex staff member when providing urine samples, but they will be told beforehand. The presence of non-nicotine, non-cannabinoid drugs of abuse or alcohol not administered experimentally in the research protocol and not detected at the time of admission will result in immediate dismissal from the research study. Food will not be permitted for 1 h prior to cocaine administration. Subjects will be prepared with an intravenous midline catheter in the non-dominant arm by the UK Healthcare Vascular Access Team (VAT). In addition, a second, standard peripheral IV will be placed by the VAT or 5N/CCTS nurse staff (if the VAT is unavailable) for the medical safety session, which requires two venous access points, and removed after that session. A peripheral IV catheter might also be necessary if issues are encountered with the midline catheter. IV access will be placed and maintained according to UKHC policies.

Drugs will be administered under double-blind conditions and medical supervision. IV cocaine will be prepared by cocaine HCl powder in 0.9% sodium chloride and administered via an FDA cleared programmable pump. Syringes containing 3 mg/70kg cocaine will be prepared from aseptically prepared stock solutions provided by the National Institute on Drug Abuse Drug Supply Program. Syringes will be prepared within 24 h of an experimental session and individually labeled for each subject. The placebo dose will contain only 0.9% sodium chloride.

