5. Drug administration. Common side effects of cocaine include anxiety, restlessness, diuresis, irritability, suppressed appetite, insomnia, gastrointestinal upset, increased heart rate, increased blood pressure, heart palpitations and

arrhythmias, faintness, irritability, shaking, headache, flushing, sweating, blurred vision, difficulty sleeping, and loss of appetite. It is likely that subjects will experience one or more of these side effects. More serious side effects following the chronic, unsupervised administration of much higher doses of cocaine have occurred and include psychotic episodes, suppressed breathing, stroke, seizures, myocardial infarctions, heart failure and death. It is unlikely that subjects will experience these more serious side effects.

7. Needle insertion and catheter maintenance. This study will require placement of an indwelling venous midline catheter to be placed for the duration of participation, and a standard peripheral IV stick for the duration of a single session, to permit intravenous saline and cocaine administration. In addition, a peripheral IV catheter might also be necessary for drug solution delivery if issues are encountered with the midline catheter. These procedures are accompanied by the risk of bruising, blood clotting, soreness, infection, bleeding, pain, swelling and irritation from the insertion of a needle. There is also a risk that the indwelling catheter could come out of the vein or penetrate the vein; if this occurs, any fluid infused into the catheter could deposit in the arm tissue, resulting in soreness, pain, swelling and irritation. Lastly, there is a risk of syncope.

SAFETY PRECAUTIONS

Protocol management forms will include prompts for research staff members to record any protocol anomalies, data collection problems, concerns with study subjects, or any unusual events that could impact the safety of the subjects or the integrity of the protocol. In addition, the PI, as well as the study physician or his appointed representative, are available at all times by telephone to respond to any questions or concerns that occur during the study. Furthermore, the PI meets with the project staff on a regular basis in the laboratory or by telephone contact to review the study activities.

Study Stopping Criteria

1. If any subject has an unexpected, serious, life threatening adverse event that is related to the study procedures, the study will be stopped.

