2. If, after 6 subjects have been enrolled and have completed at least one cocaine dosing session (33% of the proposed sample), and for all subsequent subjects, dosing was paused in greater than 33% of the cocaine dosing sessions, the study will be stopped.
3. If, after 6 subjects have been enrolled and have completed at least one cocaine dosing session, and for all subsequent subjects, greater than 33% of the study sample has been discontinued due to meeting criteria for cardiovascular hypersensitivity, the study will be stopped.

1. Violation of confidentiality.

All subject PHI is confidential and will be protected according to the guidelines established by the HIPAA. An "Authorization to use and disclose PHI for research purposes" approved by the UK IRB will be obtained. This allows the investigators on this project to use or share health information with the United States Department of Health and Human Services (DHHS) representatives, the UK IRB, the UK Office of Research Integrity (ORI), UK medical center representatives, other research collaborators or when required by law. In addition, a Certificate of Confidentiality will be issued. All data will be kept locked either on password-protected computers or in secure filing cabinets all behind locked doors and accessible only to key personnel involved in the research.

2. Embarrassment in disclosing sensitive personal information.

The risk is minimized through the use of confidentiality safeguards described above and below. Subjects can refuse to answer any questions regarding sensitive personal information, although this might impact their ability to continue in the study.

3. Discomfort due to study procedures.

Subjects are informed that they have the right to withdraw from study protocols at any time. A research staff member will always be available to answer questions, and the study subjects have telephone contact information to reach both

the PI and the study physician. If individuals become overly distressed or distraught, participation in the study is discontinued immediately, and private consultation with the study physician and/or PI is offered immediately.

4. Dissatisfaction with the study procedures.

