As noted, during the course of participation in the research, a subject could experience dissatisfaction or discomfort with the experimental procedures. A research staff member will be immediately available to address these issues, and the study subjects have telephone contact information to reach both the PI and the study physician. In addition, if individuals become overly distressed or distraught, participation in the study is discontinued immediately.

5. As described above, Drs. [name], [name] and [name] will screen all potential subjects for physical and psychiatric contraindications to participation. Urine samples will be monitored throughout each study to ensure that female subjects are not pregnant and that all subjects are adhering to the drug use restrictions. All subjects in these studies will be thoroughly informed of the various drug side-effects which they might experience and will be appropriately cautioned concerning their activities in the hours after drug administration. However, this should not pose a significant problem because research subjects will be under the direct supervision of the CRU nursing staff at all times during drug dosing. Participation is voluntary, so individuals can withdraw at any time if they find the behavioral procedures or drug effects undesirable. The drug doses to be administered in the present experiments were chosen to minimize, if not eliminate, the chance of these side effects occurring. As noted above, Drs. [name], [name] and [name] will screen all potential research subjects for medical contraindications, and [name] will review the ECG, prior to study participation. Drs. [name], [name] and [name] will monitor research subjects throughout their participation. We anticipate that careful subject selection, dose selection and subject monitoring will greatly reduce, if not eliminate, the occurrence of serious side effects. To monitor for adverse events/side effects, the Udvælg for Kliniske Undersøgelser (UKU) Side Effects Rating Scale will be completed daily with subjects by CRU nursing staff. Staff observations, subjective-effects drug effects and spontaneous subject report will also be used to monitor for adverse events.

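### Low priority: stopping criterion 3 waits for six subjects to complete a cocaine session, so on a running denominator a stop can already be certain while further subjects are dosed

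*Combined protocol and SAP*

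**What the plan says.** All three study-level rules are in Safety Precautions, Study Stopping Criteria.

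- **Item 1** has no minimum number of subjects, but needs a grave event: "If any subject has an unexpected, serious, life threatening adverse event that is related to the study procedures, the study will be stopped".
- **Item 2** concerns paused dosing sessions. It applies only after six subjects "have completed at least one cocaine dosing session (33% of the proposed sample"), which implies a planned sample of about 18.
- **Item 3** concerns hypersensitivity and has the same gate. The study stops if, once six subjects have been enrolled and have finished "at least one cocaine dosing session, and for all subsequent subjects, greater than 33% of the study sample has been discontinued" for that reason. The term *study sample* is not defined.

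At the individual level, Research Procedures says that if vital signs stay above the hypersensitivity limits on repeated and manual readings, "a subject will not receive further doses, will be followed until symptom resolution, and will be excluded from further research participation". That section also defines a rhythm criterion. Hypersensitivity is first assessed in the initial cocaine-versus-placebo session.

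The document does not say whether a subject stopped mid-session has completed that session for the purpose of the six, whether subjects are dosed one after another, or what hypersensitivity rate is expected.

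**The concern.** Because a hypersensitivity discontinuation is permanent, the number discontinued can only rise. A rule first read at a fixed point can therefore be decided before that point. Until six subjects have completed a session, items 2 and 3 are both silent, and item 1 may never be triggered by raised blood pressure or heart rate that resolves. More subjects could then receive IV cocaine although the study-level stop is already fixed. The exposure is not trivial: the first session allows up to 40 infusions of 3 mg/70 kg, and some subjects will be new to the intravenous route.

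A minimum of six is a sensible guard against stopping on 1 of 1 or 1 of 2. It gives no reason to wait once the answer at six cannot change.

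**Working it through.** **The plan's own figure.** Item 2 equates 6 subjects with 33% of the proposed sample: 6/0.33 = 18.2, so N is 18, and 6/18 = 33.3%. The plan thus writes 33% for one third, which makes one third the likelier meaning in item 3.

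**Which denominator.** Item 2 says *proposed sample* and item 3 says *study sample*. The change of term, and the re-reading for later subjects, suggest a running count of subjects dosed. They do not prove it, since a fixed denominator could also be re-read as discontinuations accrue.

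**How many discontinuations decide the first reading** (threshold one third, no one leaving for other reasons):

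| Reading | Arithmetic | Decided by | Further subjects dosed |
|---|---|---|---|
| A. Running denominator; discontinued subjects count toward six | 2/6 = 33.3%, not above one third; 3/6 = 50% | 3 | at most 3 |
| B. Running denominator; discontinued subjects do not count | 3/9 = exactly one third; 4/10 = 40% | 4 | at least 6 after four in a row |
| C. Planned 18; discontinued subjects count | 6/18 = 33.3%; 7/18 = 38.9% | 7, impossible among six | none: no gap |

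If 33% is literal, reading A needs 2 (2/6 = 33.3%), with at most 4 more dosed, and reading B needs 3 (3/9 = 33.3%).

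**How often, and how much.** The document gives no hypersensitivity rate, so p = 5%, 10%, 20% and 30% are assumed. Subjects are taken as independent and dosed in sequence, with hypersensitivity seen in the first session.

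*Reading A.* The third discontinuation falls on subject j with probability C(j−1, 2) p³ (1−p)^(j−3), and 6 − j subjects are then spared. At p = 0.20 the probabilities for j = 3, 4, 5 are 0.0080, 0.0192 and 0.0307. Their sum is 0.0579, and the mean spared is 3(0.0080) + 2(0.0192) + 1(0.0307) = 0.093.

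*Reading B.* The fourth discontinuation comes after C completers (C = 0 to 5) with probability C(3+C, C) p⁴ (1−p)^C, and on average (6−C)/(1−p) more subjects are dosed before the sixth completer. At p = 0.20 the probabilities sum to 0.0856 and the mean is 0.251.

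| Assumed rate | A: certain early | A: mean spared per study | B: certain early | B: mean spared per study |
|---|---|---|---|---|
| 5% | 0.1% | 0.002 | 0.06% | 0.001 |
| 10% | 0.9% | 0.013 | 0.8% | 0.02 |
| 20% | 5.8% | 0.093 | 8.6% | 0.25 |
| 30% | 16.3% | 0.274 | 27.0% | 1.00 |

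When the stop is certain early on reading A, 1.5 to 1.7 subjects are spared on average. With a literal 33% on reading A the means are 0.05, 0.17, 0.59 and 1.13. Overlapping enrolment, or hypersensitivity first seen in a later session, would lower all these figures.

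**The case against.** The strongest reply is that nothing is shown to be wrong: the gap rests on conditions that the document does not state, and the trigger is 3, 4, 2 or none depending on the reading. On that view the point is only a request to define two terms. The dependence on conditions stands. But on a running denominator there is a gap whether or not discontinued subjects count toward the six, and stopping once the result is certain is a change of rule as well as a definition.

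Three stronger readings are tempting, and the document does not support them.

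- *Three discontinuations always settle the rule.* They do not. A subject stopped mid-session has not literally completed it, and on that reading the first look is at 3/9, exactly one third.
- *The post-session ECG proves that discontinued subjects count.* Research Procedures requires normal rhythm for dosing to start "and to participate in further sessions (post-session ECG assessment"). Item 3 counts only subjects who meet the hypersensitivity criteria, whose rhythm limb is narrower: specified ventricular arrhythmias persisting beyond 5 minutes. Failing that ECG is not automatically an item 3 discontinuation.
- *The later subjects are dosed for nothing, or without protection.* They can still give choice data. Screening, dose pauses at limits below the exclusion limits, individual exclusion, ACLS-certified staff and item 1 all apply from the first subject.

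It is also fair that the saving is negligible at rates of 5% to 10%.

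**Conclusion.** The point holds as a low-priority, inexpensive improvement. If *study sample* means subjects dosed so far and dosing is sequential, the study-level stop can be certain while further subjects still receive IV cocaine. With 33% as one third, that is at most 3 more after three discontinuations if those subjects count toward the six, and at least 6 more after four in a row if they do not. The expected saving on the first of these readings is 0.002 to 0.27 subjects per study at assumed rates of 5% to 30%. With the planned 18 as denominator and discontinued subjects counted, there is no gap. Confidence is medium, because the document settles neither the denominator nor the counting rule. The analysis of drug choices is not in question.

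**What to change.** Reword item 3 as follows:

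1. The denominator is all subjects who have received any cocaine dose, including those stopped mid-session.
2. The threshold is more than one third, first read at six dosed and again after each later subject.
3. Add: *the study also stops as soon as 3 of the first six dosed subjects have been discontinued for cardiovascular hypersensitivity.*

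If the sponsor intends six completers with discontinued subjects not counted, use 4 discontinuations before the sixth completer. Setting 3 of the first six dosed in that case would stop some studies whose current first reading is exactly 3/9. Their share is C(6,3) p³ (1−p)⁶, or 1.1%, 4.2% and 6.4% at rates of 10%, 20% and 30%.

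**Cost.** A short rewording, an IRB amendment, and an occasional extra or earlier stop. Extra stops can arise because dosed subjects may leave for other reasons before completing a session: a drug-positive sample "will result in immediate dismissal from the research study", and "individuals can withdraw at any time if they find the behavioral procedures or drug effects undesirable". If reading A is what was meant, this needs at least three such leavers, since 3/7 = 42.9% and 3/8 = 37.5% still exceed one third and only 3/9 does not. With a 20% hypersensitivity rate and 5% to 20% leaving (all assumed), that is 0.01% to 0.4% of studies. If the sponsor meant the planned 18 as denominator, the new wording is a stricter rule, and the sponsor should confirm it before adopting it.
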